#### 2.3 Study Outcomes

The key outcomes from this study will be whether there is a significant difference in atrial strain values between NSR patients, controlled hypertensive patients and patients with either persistent or permanent AF. These electrical changes should correlate with structural changes within the LA as the LA becomes more dilated in AF patients. Furthermore, subtle differences in LA strain values may be observed between patients with PAF, persistent and permanent AF to suggest a decline in atrial strain patterns with a worsening and prolongation of AF.

This will have a significant impact to the general population as AF is the most common arrhythmia. Left atrial enlargement and dilation can occur, either as a cause or complication of AF. However, the detection of this structural change and cardiac remodelling by measuring LA area and volume is often only detected when the patient has been in AF for a prolonged period. The utilisation of speckle-tracking echocardiography (STE) and atrial strain measurements may be able to detect subtle changes in LA strain pattern which may occur before any significant cardiac remodelling and LA dilation, and thus serve as an early predictor of AF. This will allow for closer monitoring and the correct administration of anticoagulants.

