# 2. Study Outline

## 2.1 Aims and Objectives

The aims of this research project are split into two sets of comparisons. The first is to determine whether there is a statistically significant difference between atrial strain values in normal sinus rhythm (NSR) patients (control group), to controlled hypertensive patients (disease-control group) and patients with established, chronic AF (disease group). Atrial strain values from these groups will also be compared to left atrium (LA) area and volume to determine correlation. Furthermore, providing there is a significant difference, atrial strain values between AF groups PAF, persistent, and permanent can also be compared to potentiate deterioration of atrial strain.

Null hypothesis: There is no significant difference between the atrial strain measurements in patients with normal sinus rhythm to patients with chronic atrial fibrillation and no correlation between atrial strain measurements and left atrium are and volume size.

Research / alternative hypothesis: There is a statistically significant difference between atrial strain values between patients with normal sinus rhythm and patients with atrial fibrillation and this correlates with changes seen in left atrium area and volume size.

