#### 2.2.2 Study Overview

- Study design quantitative, observational, case-control study.
- Patients will be assigned to one of three groups: control group (normal sinus rhythm), disease-control group (controlled hypertension) and disease group (chronic atrial fibrillation).
- Patients will be required to visit the department on one occasion. This will be as part of either a routine or urgent referral for a transthoracic echocardiogram (TTE).
- TTEs are stored on both the ultrasound machines and computer picture archiving systems (PACS). Measurements can be taken on either the ultrasound machine or on the PACS following the patient's scan. The data obtained from these scans that will be utilised include patient demographics, heart rate and rhythm, LA area and volume measurements as well as LA strain measurements. This will be pseudo-anonymised using two Excel spreadsheets and the document will be password encrypted on a NHS OneDrive account
- Study site: within the Cardio-Respiratory department at Withybush General Hospital, there are five sonographers. This creates a throughput of approximately 60 TTE scans per week. With an expected data collection period of five months, this would equate to approximately 1200 outpatient scans factoring in annual leave and sickness. Additionally, inpatient scans can boost this number, but is dependent on current demand.

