#### 2.2.4 Eligibility Criteria

Patients must be in one of the following categories to be included: normal sinus rhythm, normal sinus rhythm with controlled hypertension and chronic atrial fibrillation (persistent or permanent). Patients with paroxysmal AF may also be included but only as part of subsequent analysis when comparing strain measurements between AF groups. Additionally, eligible patients must conform to the following inclusion and exclusion criteria.

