#### Inclusion criteria:

- Criterion 1: subjects will be included in the study if they are within one of the following groups:
  - Known to be in normal sinus rhythm, are normotensive and have no underlying health problems.
  - Known to be in normal sinus rhythm and have controlled hypertension. This must have been diagnosed by a healthcare professional and the patient should be taking appropriate antihypertensive medication.
  - Known to have chronic atrial fibrillation (persistent or permanent AF). This must have been diagnosed by a healthcare professional and the patient should be appropriately anticoagulated.
- Criterion 2: subjects should ideally be ≥ 50 years, but subjects will be age matched across all three groups.
- Criterion 3: patients should have an EF  $\ge$  50%.
- Criterion 4: good quality TTE images.
- Criterion 5: No valvular pathologies.
  - Patients with AF that have < moderate valvular pathologies may be considered (as per the British Society of Echocardiography Guidelines).

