### 2.4 Timescale

The project completion date is estimated to be March 2024 with the possibility of publishing following this. An overview of the entire project timescale can be visualised in the Gantt Chart – *see Appendix Figure 3*. The project has been split into three phases: project planning, data collection and analysis and dissertation write up and submission. The planning stage includes sponsorship and ethics approval and has an estimated completion date of May 2023. Following this, data collection and analysis may commence and in order to allow for sufficient data collection, a deadline of the end of November 2023 has been set. Furthermore, the end of January 2024 has been set to complete data analysis. The final stage consists of the write up of results, discussion and conclusion. Some of which may commence alongside data analysis and should be complete at the end of February 2024, ready for March submission. The date of the last visit for the patient will denote the end of the study. There are no follow-ups post echocardiogram required for this study, only data collection and analysis after this point.

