# 4.4 Confidentiality

For patients that wish to participate in this study, all signed Informed Consent Forms will be securely stored in the Investigator Site File within the Cardio-Respiratory Department and must not leave the department under any circumstances. The participant data will undergo pseudo-anonymisation via the use of two password-protected excel spreadsheets. One spreadsheet will contain participant numbers and corresponding hospital ID numbers. The second spreadsheet will include participant numbers along with patient demographics (i.e., sex, age, participant group, reason for patient referral, etc.). This data will be encrypted and the folder it resides in will also be encrypted and password protected. This will be stored on an NHS OneDrive account on a departmental computer. General data protection regulation (GDPR) will be maintained and followed throughout.

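### The comparison between AF types rests on one scan per patient and is not adjusted for age, so it can show a difference between types but not decline with prolonged AF

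*Combined protocol and SAP*

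**What the plan says.** **Intended reading.** Section 2.1 says that "atrial strain values between AF groups PAF, persistent, and permanent can also be compared to potentiate deterioration of atrial strain", and the objectives in the Study Summary also speak of deterioration. Sections 1.1 and 2.3 go further: differences between the types may be seen "to suggest a decline in atrial strain patterns with a worsening and prolongation of AF".

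**Design.** Section 2.2.2 has one visit per patient. Section 2.4 adds: "There are no follow-ups post echocardiogram required for this study".

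**Data.** Section 2.2.2 lists "patient demographics, heart rate and rhythm, LA area and volume measurements as well as LA strain measurements". Section 4.4 lists "patient demographics (i.e., sex, age, participant group, reason for patient referral, etc", so the list is open-ended. Neither names the date of AF onset or diagnosis, or AF duration.

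**Age control.** Under the inclusion criteria, "subjects will be age matched across all three groups". Those groups are sinus rhythm, sinus rhythm with controlled hypertension, and chronic AF, with persistent and permanent AF pooled in the last. Section 2.2.4 admits paroxysmal AF "only as part of subsequent analysis when comparing strain measurements between AF groups".

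**Analysis.** Section 2.2 runs the AF-type comparison on the data already collected, provided the main comparison is significant. Section 2.2.6 gives it a one-way ANOVA, or Kruskal-Wallis if the data are not normal, with no covariate. Section 2.2.5 sizes the three main groups and sets no number for any AF type.

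**The concern.** Decline and prolongation are statements about time. With one scan per patient, nobody's strain is seen to fall. A cross-sectional study could at best relate strain to how long each patient has had AF, and that variable is not named. AF type is a rough marker of stage, but the protocol attaches no duration to any type.

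The plan treats age as something to control in the main comparison, since it matches on it, and the Introduction says that AF becomes more common with age. That control does not reach the AF-type comparison. If the types differ in age and strain varies with age, the ANOVA picks up the age difference. At stake is a secondary finding, possibly published, that reports a contrast between patients of different ages as strain deteriorating with longer AF.

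**Working it through.** **1. Is there a variable for each part of the claim?**
- *Worsening*: AF type, an ordered but crude marker.
- *Prolongation*: none named in 2.2.2 or 4.4, and none used in 2.2.6.
- *Decline within a patient*: not observable with one visit (2.2.2, 2.4).
- *Age*: recorded (4.4) but not used in the AF-type analysis (2.2.6).

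**2. Does age matching reach the AF types?** Matching chronic AF as a whole to the two sinus-rhythm groups fixes the age of the pooled AF group. It leaves persistent and permanent patients within that group free to differ. Paroxysmal patients are in none of the matched groups.

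**3. The plan's own figure.** Inputs from 2.2.5: difference 4.0, SD 7.5, alpha 0.05, power 0.85, three groups. With equally spaced means 0, 2, 4:
- f = (4/7.5)/√6 = 0.2177
- λ = 234 × 0.2177² = 11.09
- critical F(2, 231) = 3.0349
- power = 0.8509

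This reproduces the Appendix output of 234 in total, 78 per group. It applies to the three main groups, not to the AF types.

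**4. How much could age matter?** The documents give no age slope for strain and no ages by AF type, so these inputs are assumptions chosen to show scale:
- AF type has no effect of its own.
- Strain falls by b points per year of age.
- Mean age rises evenly, by g years in total, from paroxysmal to permanent AF.
- The SD is 7.5, borrowed from 2.2.5.
- There are n patients per type. Taking n = 39 corresponds to 78 chronic AF patients split evenly (78/2) plus as many paroxysmal patients; n = 26 is a smaller case (78/3).

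The spurious gap is δ = b × g, with type means 0, −δ/2, −δ. The noncentrality is λ = n × (δ²/2)/7.5², referred to F(2, 3n − 3) at 5%. For example, with n = 39 and δ = 2, λ = 39 × 2/56.25 = 1.387, and the ANOVA rejects with probability 0.165.

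| b (points/year) | g (years) | δ (points) | Rejection rate, 39 per type | Rejection rate, 26 per type |
|---|---|---|---|---|
| 0.1 | 5 | 0.5 | 0.056 | 0.054 |
| 0.2 | 5 | 1.0 | 0.076 | 0.067 |
| 0.2 | 10 | 2.0 | 0.165 | 0.123 |
| 0.3 | 10 | 3.0 | 0.325 | 0.225 |
| 0.4 | 10 | 4.0 | 0.537 | 0.374 |

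If b = 0 or g = 0, the rate stays at 0.05. The middle of these ranges gives δ = 0.25 × 7.5 = about 1.9 points, near the third row.

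**The case against.** **The comparison is secondary, conditional and cautiously worded.** This stands, and it limits the weight of the point. A reader might infer that a stated aim of the study goes untested. The documents do not support that. Section 2.1 promises a comparison of AF types, and the ANOVA delivers one that speaks, crudely, to worsening. Prolongation appears only in 1.1 and 2.3, as an interpretation of what may be observed.

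**The age bias is assumed, not shown.** This also stands. No section says that strain falls with age or that permanent AF patients are older than paroxysmal ones. The Introduction's remark on age concerns having AF or not, and entry at 50 or over narrows the age range. A reader might infer that older age in permanent AF will produce the result; the documents show only that nothing planned would rule it out.

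**The 4.0-point gap is an extreme corner and a poor yardstick.** It needs both assumptions at their maximum. The planned 4.0 is a difference in contractile strain between AF and healthy subjects, and section 1.1 says this phase is absent in AF. Inferring that age could account for the study's whole planned effect is therefore unsupported.

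**The gap can be closed later.** In part: age is recorded and participant numbers remain linked to hospital numbers (4.4), so adjustment is possible at analysis. But an adjustment chosen after the data are seen is weaker than a planned one, and the planned wording would still claim decline.

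**A duration regression adjusted for AF type may remove the progression of interest.** Type and duration may overlap, so this stands and shapes the fix.

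**Conclusion.** The point holds for the secondary AF-type comparison. Two parts rest on the documents alone. First, with one visit and no named duration variable, the study cannot support a statement about decline over time or prolongation of AF. Second, age control does not extend to the AF types, and the planned test does not adjust for age.

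The size of any resulting bias is unknown. Under the assumptions above, the false-positive rate with 39 per type runs from about 5.6% to 53.7%, with about 16.5% near the middle; it stays at 5% if there is no age slope or no age gap. These figures show scale and do not predict the result. The main three-group comparison is unaffected by this point. The change is worth making because it costs little and prevents a possibly confounded contrast being reported as deterioration.

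**What to change.** 1. **Section 2.2.6:** in place of the unadjusted ANOVA, compare strain between AF types in a linear model (ANCOVA) with age as a covariate, and report age by AF type. If the residuals are clearly not normal, transform strain rather than fall back on Kruskal-Wallis, which again leaves age out.
2. **Sections 1.1, 2.1 and 2.3, and the matching objective in the Study Summary:** state the conclusion as a cross-sectional difference between AF types, without decline, deterioration or prolongation.
3. **Optional:** if the year of first AF diagnosis can be found in the records, add an exploratory age-adjusted regression of strain on years since diagnosis among AF participants. Show it with and without AF type, because the two may overlap.

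**Cost.** Items 1 and 2 need no new data, since age is recorded and linear regression is already in the plan. Item 3 needs one extra field. Diagnosis date only approximates onset, because AF can be silent, and it may be missing for some patients. No number per AF type is planned, so the precision of either model is unknown. Age adjustment does not remove other differences between types, such as heart rhythm at the scan, which is a further reason for the restrained wording in item 2.

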### 2.4 Timescale

The project completion date is estimated to be March 2024 with the possibility of publishing following this. An overview of the entire project timescale can be visualised in the Gantt Chart – *see Appendix Figure 3*. The project has been split into three phases: project planning, data collection and analysis and dissertation write up and submission. The planning stage includes sponsorship and ethics approval and has an estimated completion date of May 2023. Following this, data collection and analysis may commence and in order to allow for sufficient data collection, a deadline of the end of November 2023 has been set. Furthermore, the end of January 2024 has been set to complete data analysis. The final stage consists of the write up of results, discussion and conclusion. Some of which may commence alongside data analysis and should be complete at the end of February 2024, ready for March submission. The date of the last visit for the patient will denote the end of the study. There are no follow-ups post echocardiogram required for this study, only data collection and analysis after this point.

# **2.5 Publication Policy**

As findings from this study may be applicable in a much wider setting, it is important that any significant findings and benefits to patients are widely disseminated throughout research. Patients will be informed as part of the participant information document as well as verbally during their appointment regarding the intentions to possibly publish study findings. The participants are welcome to access and receive a copy of the findings and publication if they wish to do so post-study. It will be reiterated, and patients should be assured that any publishable findings will be completely anonymised and that no identifiers will be present in the publication which can link back the results to individual participants. Subjects who are not happy to have their results potentially published will be excluded from the study.

# 3. Screening, Consent and Withdrawal

# 3.1 Screening Duties

The Chief Investigator will be responsible for screening potential participants. This will be done by reviewing both in-patient and out-patient referrals to look for patients that are in one of the following categories: normal sinus rhythm, normal sinus rhythm with controlled hypertension and chronic atrial fibrillation. Subsequently, this can be further refined by excluding patients based on age, valvular pathologies and ventricular dysfunction.

# 3.2 Informed Consent Procedures

The CI will be responsible for inviting and receiving informed consent. Once potential candidates have been screened, it is envisaged that the invitation letter, PIS, ICF and a template ICF will be posted to the participant along with their appointment letter for an echocardiogram. The study team will telephone participants after they have received this information and prior to their TTE to explain the study details and to confirm whether they are interested in participating. Verbal, telephone consent can be given and recorded at this time. Written consent can also be given if the patient wishes to complete the received ICF, following the template ICF. Additionally, written consent may be given if the research team are unable to contact the patient prior to their appointment. This can be completed during the echocardiogram appointment via written informed consent. If patients are not contactable prior to their appointment, or patients contacted during their appointment wish to have more time to think about their decision, the patient may be contacted following their scan to obtain verbal, telephone consent. Similarly, if the patient is not contactable prior to their scan, and the CI is unable to discuss the study with the patient during their appointment, then again, the patient may be contacted via telephone following the TTE to obtain verbal, telephone consent. Furthermore, if a potential candidate for the study is an in-patient, after the referral has been screened, the CI will go to the appropriate ward and provide the patient with the PIS, ICF and template ICF. The study may be explained to the patient at this time or at the time of the scan and only written informed consent can be given in this instance. Participants will be enrolled into the study once verbal or written consent have been given. If telephone consent is obtained, a copy of the signed consent form will be provided to the participant - either during their appointment visit or via post following the scan.

It will be explained to patients that they have been identified as potential candidates for this study and a lay summary will be provided to outline the research project. The patient should be reassured that the scan will not differ because of their involvement in the study and there will be no delay in the results and TTE report as a result. The patient should also be informed that if they choose not to participate in the research study, this will not affect their standard of care in any way. Participants will be encouraged to ask questions and they will have the right to decline to take part in the study without providing any reasons. It should be explained to the patient that it is highly unlikely that there will be any incidental findings. However, any incidental findings would be dealt with accordingly, as they usually would as per standard of care, and would be reported back to the referring clinician. Unless GPs are the initial echocardiogram refer, they will not be directly contacted regarding incidental findings but should have access to patient information and testing using the Welsh Patient Administration System and Welsh Clinic Portal system. The cardio-respiratory department does not have any direct contact or involvement with life insurance companies, however, if a patient has already been referred for an echocardiogram, it could be argued that they are currently awaiting investigations regardless of their involvement in the study.

## **3.3 Study Withdrawal**

Not all patients that provide written informed consent to be involved in this study will be deemed to be suitable and thus will not be included. If it is deemed that the quality of the TTE images obtained are not of a high enough quality (LA and LA walls must be fully visible and clear), then the subject will not be included in the study. This is because unclear images make it very difficult to accurately measure the LA area and volume. Clear LA wall borders are required to obtain atrial strain measurements. Including unclear images in the study will not provide an accurate measurement of LA strain for comparison. This will be explained to the patient prior to receiving consent and in the participant information sheet. The patient should be reassured that if their images are deemed to be of an inadequate standard for LA strain analysis, this does not mean that they do not have a diagnostic use as per referral request.

Participants have a right to withdraw their consent at any point in the study. As the data will have been pseudo-anonymised, if consent withdrawal is following data collection, the data obtained thus far must be uncovered to match the patient identifiers which are to be kept separately from patient data. Once the patient's data has been correctly identified, this will be removed from records and not included in any data analysis. However, if the participant chooses to withdraw following any processing of data, it may not be possible to remove this data from the analysis.

# 4. Risk, Ethical Considerations and Confidentiality

## 4.1 **Risks and Benefits**

This research study is very low risk. TTEs have no known associated risks. Some pressure is applied during the scan to obtain images, and this may be sensitive for some patients, however, this is the case regardless of the study. The potential benefit of this study is that participants may be identified as having atrial strain patterns which are similar to those seen in patients with AF or may be an early predictor of AF. If this is the case, the patient can be monitored more closely and appropriately medicated if required.

